12.3 Reporting of Adverse Events

- When “severe adverse events” or “unexpected adverse events” occur, the Research Responsible Person of research participating unit should report them to the Research Committee.
- Based on the relevant laws and regulations, adverse events should be reported to the province (city) Health Department at the location of the research center. Severe adverse events based on clinical research-related ethical guideline should be reported to the person in overall charge of the medical institution. The appropriate reporting procedures should be completed in accordance with the relevant provisions of all medical institutions at the same time. The person in charge of research of the research participating unit should hold accountability and responsibility for the emergency treatment of patients with any degree of adverse

events to ensure patient safety.

12.3.1 Adverse Events with Reporting Obligations

12.3.1.1 Adverse Events with Emergency Reporting Obligations

Any of the following adverse events should be reported on an emergent basis:

- All patients who die during the course of treatment or within 30 days from the last treatment day, regardless of the presence or absence of a causal relationship with the study regimen treatment. Also, cases of discontinuation of treatment, even if within 30 days from the last treatment day, those patients are also emergent reporting objects. (“30 days” refers to day 0, the final treatment day, 30 days starting from the next day)
- Those patients with unexpected Grade 4 non-hematologic toxicity (CTCAE v3.0 adverse events other than the blood/bone marrow group), having a causality of treatment (any of definite, probable, possible) who emergent reporting objects are.

12.3.1.2 Adverse Events with Regular Reporting Obligations

One of the following adverse events are regular reporting objects:

- (1) After 31 days from the last treatment day, deaths for which a causal relationship with treatment cannot be denied, including suspected treatment-related death; death due to obvious primary disease is included.
- (2) Expected Grade 4 non-hematologic toxicity (CTCAE v3.0 adverse events other than the blood/bone marrow group).
- (3) Unexpected Grade 3 adverse events: Grade 3 adverse events are not recorded in the 12.1 expected adverse events.
- (4) Other significant medical events: adverse events that the study group deems cause important and potentially permanent, significant impact on their offspring (MDS myelodysplastic syndrome, except for secondary cancer) Adverse events among above (2)-(4), determined to have a causal relationship (any of definite, probable, possible) with the study regimen are regular reporting objects.

12.3.2 Reporting Procedure

12.3.2.1 Emergency Reporting

- In case of any adverse event on emergency study reporting objects, the doctor in charge will quickly report it to the Research Responsible Person of the research participating hospitals. When the Research Responsible Person of the hospital cannot be contacted, the coordinator or the doctor in charge of the hospital must

assume the responsibility on behalf of the Research Responsible Person of the hospital.

- **First Reporting:** Within 72 hours after the occurrence of adverse events, the Research Responsible Person of the hospital should complete the “AE/AR/ADR first emergency report” and send it to the Research Committee by email and telephone.
- **Second Reporting:** The research responsible person of the research participating hospital completes the “AE/AR/ADR Report” and a more detailed case information report (A4 format), and then faxes the two reports to the Research Committee within 15 days after the occurrence of adverse events. If any autopsy examination, the autopsy result report should be submitted to the Research Committee.

12.3.2.2 General Reports

- The research responsible person of research participating hospital completes the “AE/AR/ADR report”, and then faxes it to the Research Committee within 15 days after the occurrence of adverse events.

12.5 Review of Efficacy and Safety Evaluation Committee

The Efficacy and Safety Evaluation Committee reviews and discusses the report in accordance with the procedures recorded in the *Clinical Safety Information Management Guideline*, and makes recommendations in writing for the Research Responsible Person, including whether to continue to include study objects or to modify the study protocol.

13 Ethical Considerations

13.1 Responsibilities of researchers

The investigators are responsible for the conduction of this study. The investigators will ensure the implementation of this study in accordance with the study protocol and in compliance with the Declaration of Helsinki, as well as domestic and international ethical guiding principles and applicable regulatory requirements. It is specially noted that, the investigators must ensure that only subjects providing informed consent can be enrolled in this study.

13.2 Information and Informed Consent of Subjects

An unconditional prerequisite for subjects to participate in this study is his/her written informed consent. The written informed consent of subjects participating in this study must be given before study-related activities are conducted.

Therefore, before obtaining informed consent, the investigators must provide sufficient information to the subjects. In order to obtain the informed consent, the investigators will provide the information page to subjects, and the information required to comply with the applicable regulatory requirements. While providing written information, the investigators will orally inform the subjects of all the relevant circumstances of this study. In this process, the information must be fully and easily understood by non-professionals, so that they can sign the informed consent form according to their own will on the basis of their full understanding of this study.

The informed consent form must be signed and dated personally by the subjects and investigators. All subjects will be asked to sign the informed consent form to prove that they agree to participate in the study. The signed informed consent form should be kept at the research center where the investigator is located and must be properly safe kept for future review at any time during audit and inspection throughout the inspection period. Before participating in the study, the subjects should provide a copy of signed and dated informed consent form.

At any time, if important new information becomes available that may be related to the consent of the subjects, the investigators will revise the information pages and any other written information which must be submitted to the IEC/IRB for review and approval. The revised information approved will be provided to each subject participating the study. The researchers will explain the changes made to the previous version of ICF to the subjects

13.3 Identity and Privacy of Subjects

After obtaining an informed consent form, each selected subject is assigned a subject number (Allocation Number). This number will represent the identity of the subject during the entire study and for the clinical research database of the study. The collected data of subjects in the study will be stored in the ID.

Throughout the entire study, several measures will be taken to minimize any breaches of personal information, including: 1) only the investigators will be able to link to the research data of the subjects to themselves through the identify table kept at the research center after authorization; 2) during onsite auditing of raw data by the supervisors of this study, as well as relevant inspection and inspection visits by the supervision departments, the personnel engaging in the above activities may view the original medical information of subjects that will be kept strictly confidential.

Collection, transmission, handling and storage of data on study subjects will comply with the data protection and privacy regulations. This information will be provided to the study subjects when their informed consent is being obtained for treatment procedures in accordance with national regulations.

13.4 Independent Ethics Committee or Institutional Review Committee

Before beginning the study, the research center will be responsible for submitting the study protocol and relevant documents (informed consent form, subject information page, CRF, and other documents that may be required) to the Independent Ethics Committee (IEC)/ Institutional Review Board (IRB) to obtain their favorable opinion/approval. The favorable opinions/approval documents of the IEC/IRB will be archived in the research center folders of the investigators.

Before beginning the study at the center, the investigators must obtain written proof of favorable opinions/approval by the IEC/IRB, and should provide written proof of the date of the favorable opinions/approval meeting, written proof of the members presenting at the meeting and voting members, written proof of recording the reviewed study, protocol version and Informed Consent Form version, and if possible, a copy of the minutes.

In case of major revisions to this study, the amendment of the study protocol will be submitted to the IEC/IRB prior to performing the study. In the course of the study, the relevant safety information will be submitted to the IEC/IRB in accordance with national regulations and requirements.

13.5 Supervising

The research approach of the authorities and any associated files (such as the research protocol, subjects' informed consent) will be in accordance with the requirements of the ethical review board of biomedical research involving humans (Trial) (2007) and the applicable Chinese laws and regulations. Studies should provide the main references or inform the ethics review guidance advisory organization of the provincial health administrative department in the province the research center is in.

14 Organizations and Responsibilities of Study

14.2 Efficacy and Safety Evaluation Committee

Responsible for the supervision/monitoring of treatment safety and efficacy of this study.

- Person in Charge of Efficacy and Safety Evaluation Committee: [name] (Department of General Surgery and Center of Microinvasive Gastrointestinal Surgery, Southwest Hospital, China)

16.2 Definitions involved in SOP

16.2.1 ECOG performance status score

According to the simplified performance status score scale developed by the ECOG, the patients' performance status can be classified into 6 levels, namely 0-5, as follows:

0: Fully active, able to carry on all pre-disease performance without restriction

1: Restricted in physically strenuous activity but ambulatory and able to carry out work of a light or sedentary nature, e.g., light housework, office work

2: Ambulatory and capable of all self-care but unable to carry out any work activities. Up and about more than 50% of waking hours

3: Capable of only limited self-care, confined to bed or chair more than 50% of waking

hours

4: Completely disabled. Cannot carry on any self-care. In total, confined to bed or chair

5: Dead

Patients at levels 3, 4 and 5 are generally considered to be unsuitable for surgical treatment or chemotherapy.

16.2.2 ASA classification

According to the patients' physical status and surgical risk before anesthesia, the American Society of Anesthesiologists (ASA) has categorized patients into 5 levels (I-V levels):

Class I: Well-developed patients with physical health and normal function of various organs, with a perioperative mortality rate of 0.06% -0.08%.

Class II: Patients with mild complications and good functional compensation in addition to surgical diseases, with a perioperative mortality rate of 0.27% -0.40%.

Class III: Patients with severe complications and restricted physical activity but still capable of coping with day-to-day activities, with a perioperative mortality rate of 1.82% -4.30%.

Class IV: Patients with serious complications who have lost the ability to perform day-to-day activities, often have life-threatening conditions, and a perioperative mortality rate of 7.80% -23.0%.

Class V: Moribund patients either receiving surgery or not, have little chance for survival, and a perioperative mortality rate of 9.40% -50.70%.

Generally, Class I/II patients are considered good for anesthesia and surgical tolerance, with a smooth anesthesia process. Class III patients are exposed to some anesthesia risks; therefore, good preparations should be fully made before anesthesia, and effective measures should be taken to prevent potential complications during anesthesia. Class IV patients are exposed to the most risks, even if good preoperative preparations are made, and have a very high perioperative mortality rate. Class V patients are moribund patients and should not undergo an elective surgery.

16.2.3 Oncology-related definitions

In this study, tumor staging is based on AJCC-8; surgical treatment follows the Japanese Gastric Cancer Treatment Guidelines, Physicians Edition, 4rd Edition, 2014.05, and other writing and recording principles follow the Japanese Gastric Cancer Statute 15th.

16.2.4 Primary focus location

The greater and lesser curvature of the stomach are divided into three equal parts, the U (upper), M (middle) and L (lower) areas, connected to the corresponding points. If the lesions are located

in two or more adjacent areas, they should be recorded in the order of the main portions of the lesions. Esophagogastric junction carcinoma is defined as a tumor whose tumor center is located within 5cm above and below the esophagogastric junction. According to Siewert classification, the tumor was divided into Siewert type I : the tumor center was located 1 ~ 5 cm above the esophagogastric boundary; Siewert type II : The center of the tumor was 1 cm to 2 cm above the esophagogastric boundary. Siewert type III : The tumor center is located 2 to 5 cm below the esophagogastric boundary.

[figure not shown]

Fig. 1 The three portions of the stomach. *U* upper third, *M* middle third, *L* lower third, *E* esophagus, *D* duodenum

[figure not shown]

Fig. 2 The four equal parts of the gastric circumference. *Less* lesser curvature, *Gre* greater curvature, *Ant* anterior wall, *Post* posterior wall

[figure not shown]

Fig. 3. Siewert type
16.2.5 Tumor staging record
16.2.5.1 Recording principle

The two staging records for clinical classification and pathological classification involve T (invasion depth), N (regional lymph node) and M (distant metastasis), which are expressed in Arabic numerals and denoted as x if indefinite.

Clinical classification	Pathological classification
Physical examination X-ray, endoscopy, diagnostic imaging laparoscopy, intraoperative observations (laparotomy/laparoscopy), biopsy, cytology, biochemistry, biology examination	Pathological diagnosis of the endoscopic/surgical specimens Intraperitoneal exfoliative cytology

16.2.5.2 Records of tumor invasion depth

Tumor invasion depth is defined as follows:

TX: Unknown cancer invasion depth

T0: No cancer found

T1: Cancer invasion is only confined to the mucosa (M) or the submucosal tissue (SM)

◆ T1a: Cancer invasion is only confined to the mucosa (M)

- ◆ T1b: Cancer invasion is confined to the submucosal tissue (SM)

T2: Cancer invasion exceeds the submucosal tissue but is only confined to the inherent muscular layer (MP)

T3: Cancer invasion exceeds the inherent muscular layer (MP) but is only confined to the subserosal tissue (SS)

T4: Cancer invasion involves the serosa (SE) or direct invasion of adjacent structures (SI)

- ◆ T4a: Cancer invasion involves only the serosa (SE)

- ◆ T4b: Cancer directly invades the adjacent structures (SI)

16.2.5.3 Records of tumor metastasis

(1) Lymph node metastasis:

NX: Number of lymph node metastases is unknown

N0: No lymph node metastasis

N1: Lymph node metastasis of 1-2 areas

N2: Lymph node metastasis of 3-6 areas

N3: Lymph node metastasis of 7 and more areas

- ◆ N3a: Lymph node metastasis of 7-15 areas

- ◆ N3b: Lymph node metastasis of 16 and more areas

Lymph node numbers are defined as follows:

[figure not shown]
No.	Name	Definition
1	Cardia right	Lymph nodes around the gastric wall first branch (cardia branch) of ascending branches of the left gastric artery and those at the cardia sides
2	Cardia left	Lymph nodes at the left side of the cardia and those along the cardia branch of the lower left diaphragmatic artery esophagus
3a	Lesser gastric curvature (along the left gastric artery)	Lymph nodes at the lesser curvature side along the left gastric artery branch, below the cardia branch
3b	Lesser gastric curvature (along the right gastric artery)	Lymph nodes at the lesser curvature side along the right gastric artery branch, partial left side of the 1st branch in the lesser curvature direction
4sa	Left side of the greater gastric curvature (short gastric artery)	Lymph nodes along the short gastric artery (excluding the root)

[figure not shown]
Study protocol

4sb	Left side of the greater gastric curvature (along the left gastroepiploic artery)	Lymph nodes along the left gastroepiploic artery and the first branch of the greater curvature (refer to the definition of No. 10)
4d	Right side of the greater gastric curvature (along the right gastroepiploic artery)	Lymph nodes at the partial left side of the first branch in the greater gastric curvature direction along the right gastroepiploic artery
5	Superior pylorus	Lymph nodes along the right gastric artery and around the first branch in the lesser gastric curvature direction
6	Inferior pylorus	Lymph nodes from the root of the right gastroepiploic artery to the first branch in the greater gastric curvature direction and those at the junction of the right gastroepiploic veins and superior anterior pancreaticoduodenal veins (including the junction portion)
7	Left gastric artery trunk	Lymph nodes from the root of the left gastric artery to the branch portion of the ascending branches
8a	Anterior upper part of the common hepatic artery	Lymph nodes at the anterior upper part of the common hepatic artery (from the branch portion of the splenic artery to the branch portion of the gastroduodenal artery)
8p	Posterior part of the common hepatic artery	Lymph nodes at the posterior part of the common hepatic artery (from the branch portion of the splenic artery to the branch portion of the gastroduodenal artery)
9	Surrounding of the celiac artery	Lymph gland that is in the surroundings of the celiac artery or that is a part of each root of the left artery of the stomach, common hepatic artery and splenic artery as well as that related to the celiac artery
10	Splenic hilum	Lymph gland that is in the surroundings of the celiac artery and splenic hilum far away from the end of the pancreas, including the first greater gastric curvature in the root of the short gastric artery and the left gastroepiploic artery
11p	Splenic artery proximal	Lymph gland at the splenic artery proximal (in a location that divides the distance between the root of the splenic artery and the end of the pancreas into two equal parts, including the proximal side)
11d	Splenic artery distal	Lymph gland at the splenic artery distal (in a location that divides the distance between the root of the splenic artery and the end of the pancreas into two equal parts, inclining to the end of the pancreas)
12a	Within the hepatoduodenal	Lymph gland that is below a location that divides the height of the confluence portions of the left and right hepatic ducts and the bile

	ligament (along the proper hepatic artery)	duct in the upper margin of the pancreas into two equal parts and is along the proper hepatic artery (as stated in No. 12a2 of the regulations for bile duct carcinoma)
12b	Within the hepatoduodenal ligament (along the bile duct)	Lymph gland that is below a location that divides the height of the confluence portions of the left and right hepatic ducts and the bile duct in the upper margin of the pancreas into two equal parts and is along the proper hepatic artery (as stated in No. 12b2 of the regulations for bile duct carcinoma)
12p	Within the hepatoduodenal ligament (along the portal vein)	Lymph gland that is below a location that divides the height of the confluence portions of the left and right hepatic ducts and the bile duct in the upper margin of the pancreas into two equal parts and is along the proper hepatic artery (as stated in No. 12p2 of the regulations for bile duct carcinoma)
13	Back of the pancreatic head	Lymph gland adjacent to the head of the duodenal papilla at the back of the pancreatic head (No. 12b in the surroundings of the hepatoduodenal ligament)
14v	Along the superior mesenteric vein	Lymph gland that is in the front of the superior mesenteric vein, with the inferior margin of the pancreas on the upper side, the right gastroepiploic vein and confluence portion of the superior pancreaticoduodenal vein to the right, the left margin of the mesenteric vein to the left and the branch of the middle colic vein in the lower margin
14a	Along the superior mesenteric artery	Lymph gland along the superior mesenteric artery
15	Surroundings of the colon middle artery	Lymph gland that is in the surroundings of the colon middle artery
16a1	Surroundings of the abdominal aorta a1	Lymph gland that is in the surroundings of the aorta gap (4 to 5 cm wide in the surroundings of the medial crus of the diaphragm)
16a2	Surroundings of the abdominal aorta a2	Lymph gland that is in the surroundings of the aorta from the upper margin of the abdominal artery root to the lower margin of the left renal vein
16b1	Surroundings of the abdominal aorta b1	Lymph gland that is in the surroundings of the aorta from the lower margin of the left renal vein to the upper margin of the inferior mesenteric artery root
16b2	Surroundings of the abdominal aorta b2	Lymph gland that is in the surroundings of the aorta from the upper margin of the inferior mesenteric artery root to the branch of aorta
17	Front of the	Lymph gland that is in the front of the pancreatic head, next to the

	pancreatic head	pancreas and under the pancreatic capsule
18	Below the pancreas	Lymph gland that is in the lower margin of the pancreas
19	Below the diaphragm	Lymph gland that is in the cavity of the diaphragm and along the lower side of the diaphragmatic artery
20	Hiatal part of the gullet	Lymph gland that connects the hiatal part of diaphragm to the gullet
110	Beside the lower gullet	Lymph gland that departs from the diaphragm and is next to the lower gullet
111	Above the diaphragm	Lymph gland that is in the cavity of the diaphragm and departs from the gullet (No. 20 that connects to the diaphragm and gullet)
112	Posterior mediastinum	Lymph gland of the posterior mediastinum departed from the gullet and its hiatal portion

血管名

略字説明

APIS *A. phrenica inferior sinistra*
 AGB *Aa. gastricae breves*
 AGES *A. gastroepiploica sinistra*
 VGED *V. gastroepiploica dextra*
 VCDA *V. colica dextra accessoria*
 VCM *V. colica media*
 TGC *Truncus gastrocolicus*
 ACM *A. colica media*
 AJ *A. jejunalis*

AHC *A. hepatica communis*
 VP *V. portae*
 VL *V. lienalis*
 VMS *V. mesenterica superior*
 VPDSA *V. pancreaticoduodenalis superior anterior*
 VCD *V. colica dextra*
 VJ *V. jejunalis*
 AGP *A. gastrica posterior*
 ACD *A. colica dextra*

Fig. 4. Lymph node grouping

(2) Distant metastasis

M0: No distant metastasis outside of the regional lymph nodes

M1: Distant metastasis outside of the regional lymph nodes

MX: Presence of distant metastasis is unclear

Record the specific sites under the M1 condition: peritoneum (PER), liver (HEP), lymph node (LYM), skin (SKI), lung (PUL), bone marrow (MAR), bone (OSS), pleura (PLE), brain (BRA) and meninges (MEN), intraperitoneal exfoliated cells (CY), and others (OTH). Note: A positive examination result for intraperitoneal exfoliated cells is recorded as M1.

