8.3.2.2 Lymph node metastasis

- The number of lymph nodes in each group was used as the denominator, the number of lymph nodes in the final pathological report was used as the molecule, and the proportion of lymph node metastasis in each group was obtained. The proportion of total gastric lymph node metastasis was calculated

9 Standard operating procedures (SOP)

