9.3.1.5 Regulations on the extent of the Lymph node dissection

Follow the Japanese gastric cancer treatment guidelines 2014 (ver. 4): Total gastric resection with D2 Lymphadenectomy (No. 1,2,3,4,5,6,7,8a,9,10,11,12a).

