9.5 Post-operative adjuvant therapy

9.5.1 Indications for postoperative adjuvant chemotherapy

After completion of the surgical treatment, according to the postoperative pathological results, subjects among the R0 resection cases that are stage II and above are administered postoperative adjuvant chemotherapy according to the provisions of this program.

For cases of non-R0 resection or recurrence after R0 resection, this study does not

stipulate the follow-up treatment plan; the research center decides on the action to be taken according to the clinical treatment routine.

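### The N categories are cut by an undefined count of areas that conflicts with the protocol's own node counts, and the nodal metastasis proportion has a numerator that does not measure metastasis

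*Protocol*

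**What the plan says.** Two definitions are at issue, both in the protocol.

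**N category (16.2.5.3).** The list opens with "NX: Number of lymph node metastases is unknown" and then changes unit: "N1: Lymph node metastasis of 1-2 areas", "N2: Lymph node metastasis of 3-6 areas", "N3a: Lymph node metastasis of 7-15 areas" and "N3b: Lymph node metastasis of 16 and more areas". The word *areas* is not defined for nodes. A table of numbered stations follows. The stage table in 16.2.5.4 has a filled column for each of N0, N1, N2, N3a and N3b.

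**Metastasis proportion (8.3.2.2).** The denominator is the number of nodes in each group. For the numerator, "the number of lymph nodes in the final pathological report was used as the molecule". The result is called the proportion of lymph node metastasis, by group and in total.

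**Related text.**
- Section 9.3.1.5 sets the dissection: "Total gastric resection with D2 Lymphadenectomy (No. 1,2,3,4,5,6,7,8a,9,10,11,12a".
- Section 9.3.4, item (1), records total nodes, nodes per group, metastatic nodes per group and total metastases.
- Section 5.2 lists harvested and metastatic node numbers as a secondary outcome.
- Sections 6 and 16.2.3 name AJCC 8th edition as the staging system.
- Section 9.5.1 uses stage: "subjects among the R0 resection cases that are stage II and above are administered postoperative adjuvant chemotherapy".

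**The concern.** A staging rule needs one unit. Here the row for unknown status counts metastases and the rows for known status count something else, which is undefined and has no matching item in the pathology record. Anyone deriving stage from the annex has to guess. The nearest thing to an area in the text is a numbered station, and on that guess the top category is practically empty although the stage table provides for it.

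The proportion in 8.3.2.2 has a different fault: it never uses the metastatic count. It stands in the section that defines end points, so a programmer could implement it as it reads.

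At stake are the recorded pathological stage, the stage condition in 9.5.1, and a derived nodal figure that might be reported for both arms. Because the arms are not randomised, readers will probably look at stage when they judge comparability.

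**Working it through.** **1. How many areas are available?** Section 9.3.1.5 lists stations 1, 2, 3, 4, 5, 6, 7, 8a, 9, 10, 11 and 12a, which is 12. The annex table splits 3 into 3a/3b, 4 into 4sa/4sb/4d and 11 into 11p/11d, which adds 1 + 2 + 1 = 4, giving 16. The N3b cut-off is 16 or more. With 12 stations N3b is impossible within the prescribed field. With 16 it requires every sub-station to be positive.

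**2. Direction of the discrepancy.** Each involved station contains at least one involved node, so

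involved stations ≤ involved nodes.

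The cut-offs (1-2, 3-6, 7-15, 16+) are the same numbers under either unit. The station-based N is therefore equal to or lower than the node-based N, never higher.

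**3. Effect on stage, read from 16.2.5.4.**

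| Case | By stations | By nodes |
|---|---|---|
| T3, 10 nodes in 2 stations | N1, IIB | N3a, IIIB |
| T3, 16 nodes in 6 stations | N2, IIIA | N3b, IIIC |
| T2, 3 nodes in 1 station | N1, IIA | N2, IIB |
| T1, 4 nodes in 2 stations | N1, IB | N2, IIA |
| T4a, 4 nodes in 2 stations | N1, IIIA | N2, IIIA |

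The last row shows that a change of N need not change the stage. In the T4b row, N1 and N2 are both IIIB, and N3a and N3b are both IIIC.

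**4. The stage II threshold in 9.5.1.** The lowest node-positive stages are T2N1 = IIA, T3N1 = IIB, T4aN1 = IIIA and T4bN1 = IIIB. All are stage II or above under either unit. Only T1N1 = IB lies below. A patient changes side only with pT1 and 3 or more positive nodes confined to 1 or 2 stations. Such patients can occur: the summary defines entry by clinical stage (cT2-4a), and the withdrawal criteria in 4.3 name T4b and M1 but not pathological T1.

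**5. How often could N differ?** The protocol gives no distribution of nodes over stations. As an illustration only, assume that positive nodes fall independently and uniformly over *S* stations. With 3 or with 7 nodes, N drops whenever any two share a station:

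P(lower N) = 1 − S(S−1)…(S−m+1)/S^m

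- m = 3: 1 − 1,320/1,728 = 24% (S = 12); 1 − 3,360/4,096 = 18% (S = 16).
- m = 7: 1 − 3,991,680/35,831,808 = 89% (S = 12); 1 − 57,657,600/268,435,456 = 79% (S = 16).

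Clustering would raise these figures, and a limited number of nodes per station would lower them. They show sensitivity near a cut-off and are not estimates for this trial.

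**6. The proportion in 8.3.2.2.** Let *n_s* be the nodes reported for station *s*, *m_s* the metastatic ones, and *n* the total.

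- Numerator taken station by station: n_s / n_s = 1, whatever m_s is.
- Numerator taken as the whole-report count: n / n_s, which exceeds 1 whenever another station also has nodes.
- Evidently intended: m_s / n_s, and Σm_s / Σn_s in total.

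With an assumed 40 nodes examined and 0, 4 or 10 positive, the intended total is 0%, 10% or 25%. The text as written gives 40/40 = 100% each time.

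**The case against.** The best defence is that these are translation slips that nobody would apply. The protocol never equates areas with stations, and elsewhere it calls stations groups. The NX row points to a count of metastases, and a named staging system governs. That an N3b of 16 stations is absurd is itself evidence that another meaning was intended. In 8.3.2.2, the heading and the name of the result make the missing word plain.

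Much of this stands, and it rules out several stronger readings that a reader might infer.

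- *That patients will be understaged.* This needs areas to mean stations and the annex to be applied literally. The protocol supports the first only as a natural guess and says nothing on the second.
- *That stage changes for every patient whose N changes.* The T4a row already contradicts this.
- *That eligibility under 9.5.1 is broadly altered.* Step 4 confines it to one narrow pT1 group, whose frequency is not given.
- *That a stage imbalance between arms would be hidden in the analysis.* Section 10.1 describes no analysis by pathological stage, and the baseline list in 9.1.1 does not include it.
- *That the proportion is exactly 100% for everyone.* It can also exceed 100%, depending on how the numerator is matched.

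The defence does not remove the inconsistency. The annex changes unit within one list and leaves the new unit undefined, and the text of the named staging manual is not in the protocol to settle it. Evident intent is no substitute for a correct formula in an end-point section.

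**Conclusion.** The point holds as a definitional inconsistency with limited reach. The unit of the N categories conflicts with the NX row, with the recorded node counts and with the extent of dissection. On the station reading, which is an assumption, the error runs only downwards, by as much as IIB against IIIB in the T3 example. The finding on 8.3.2.2 needs no such assumption: on either matching of the numerator, the ratio does not measure metastasis.

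The primary outcome, the sample size and the secondary outcome of harvested and metastatic node numbers depend on neither definition. The proportion in 8.3.2.2 is not itself a listed outcome in 5.1 or 5.2. The text should be corrected before stage and nodal figures are derived, but it does not threaten the main comparison.

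**What to change.** 1. Reconcile the N list in 16.2.5.3 with its own NX row, the staging system named in sections 6 and 16.2.3, the counts recorded in 9.3.4 and the table in 16.2.5.4, so that one defined unit runs from NX to N3b for recorded pathological stage.
2. In 8.3.2.2, set the numerator to metastatic nodes in the final pathology report and the denominator to nodes examined, per station and in total. State that group there means station, and say what is reported for a station with no nodes examined.
3. The sponsor should then reconcile how the stage condition in 9.5.1 applies. That is a clinical matter on which this point takes no position.

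The cost is wording only. Section 9.3.4 already collects nodes and metastatic nodes per group and in total, so no new data are needed. Any stage already derived by counting areas can be recalculated from those records.
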